## 7 Trial Procedures

### 7.1 Trial Procedures

The Trial Flow Chart - Section 6.0 summarizes the trial procedures to be performed at each visit. Individual trial procedures are described in detail below. It may be necessary to perform these procedures at unscheduled time points if deemed clinically necessary by the investigator.

Furthermore, additional evaluations/testing may be deemed necessary by the Sponsor and/or CheckMate for reasons related to subject safety. In some cases, such evaluation/testing may be potentially sensitive in nature (e.g., HIV, Hepatitis C, etc.), and thus local regulations may require that additional informed consent be obtained from the subject. In these cases, such evaluations/testing will be performed in accordance with those regulations.

#### 7.1.1 Treatment period

The study consists of 3 main phases:

- **Prime Phase (Weeks 1-7):**
  - Nivolumab (240 mg) I.V. infusion every 2 weeks for 3 doses (starting 2nd week of CMP-001 administration – W2D1) given concurrently with CMP-001.
  - CMP-001 will be administered subcutaneously (week 1), then intra-tumorally (weeks 2-7) on a weekly schedule.
- **Definitive Surgery:** Follows completion of prime phase.
- **Boost Phase (following recovery from surgery) (Weeks 12-56):**
  - Nivolumab (240 mg I.V. infusion every 2 weeks; or 480 mg I.V infusion every 4 weeks) given concurrently with CMP-001 5mg every 4 weeks.
  - CMP-001 will be administered subcutaneously (peri-tumoral resection site).
  - Total of 12 doses of CMP-001 will be administered.
  - Total of 46 weeks of Nivolumab will be administered (every 2 weeks - 23 doses; every 4 weeks – 12 doses).

#### 7.1.2 Administrative Procedures

Informed consent must be documented by the subject's dated signature or by the subject's legally acceptable representative's dated signature on a consent form along with the dated signature of the person conducting the consent discussion prior to enrollment.

During initial enrollment visit, study investigator (or designee) must discuss the following with patients:

- Inclusion and exclusion criteria
- Medical history – pertinently any condition diagnosed within the prior 10 years that are considered to be clinically significant by the Investigator.
- Prior and concomitant medications. All medications related to reportable SAEs and ECIs should be recorded as defined in **Section 7.2**.
- Disease details and treatments.

#### 7.1.3 Clinical Procedures/Assessments

##### 7.1.3.1 Adverse event (AE) monitoring

The investigator or qualified designee will assess each subject to evaluate for potential new or worsening AEs as specified in the Trial Flow Chart and more frequently if clinically indicated. Adverse experiences will be graded and recorded throughout the study and during the follow-up period according to NCI CTCAE Version 4.0 (see Section 12.2). Toxicities will be characterized in terms regarding seriousness, causality, toxicity grading, and action taken with regard to trial treatment.

All AEs of unknown etiology associated with nivolumab exposure should be evaluated to determine if it is possibly an event of clinical interest (ECI) of a potentially immunologic etiology (irAE). See **Section 5.6.1.1** regarding the identification, evaluation and management of AEs of a potential immunological etiology.

Related and clinically significant AEs occurring within 30 days after the last dose of study drug should be recorded. Patients who are discontinued from the study due to an unacceptable drug-related AE will be followed until the resolution of the AE to Grade 0-1 or stabilization or until initiation of a new therapy for their cancer, whichever occurs first. Related SAEs that occur within 90 days of the end of treatment or before initiation of a new antineoplastic treatment should also be followed and recorded.

Please refer to section 7.2 for detailed information regarding the assessment and recording of AEs.

#### **7.1.3.2 Full physical exam**

The investigator or qualified designee will perform a complete physical exam during the screening period. Clinically significant abnormal findings should be recorded as medical history. A full physical exam should be performed during screening.

#### **7.1.3.3 Directed physical exam**

For visits that do not require a full physical exam per the Trial Flow Chart, the investigator or qualified designee will perform a directed physical exam as clinically indicated prior to trial treatment administration.

#### **7.1.3.4 Vital signs**

The investigator or qualified designee will take vital signs at screening, prior to the administration of each dose of trial treatment and at treatment discontinuation as specified in the Trial Flow Chart (Section 6.1). Vital signs should include temperature, pulse, respiratory rate, weight and blood pressure. Height will be measured at screening only.

#### **7.1.3.5 Eastern Cooperative Oncology Group (ECOG) performance scale**

The investigator or qualified designee will assess ECOG status (see Section 12.4) at screening, prior to the administration of each dose of trial treatment and discontinuation of trial treatment as specified in the Trial Flow Chart.

#### **7.1.3.6 Tumor imaging and assessment of disease**

Response and progression will be evaluated in this study using the international criteria proposed by the Response Evaluation Criteria in Solid Tumors (RECIST v.1.1) Committee [Eisenhauer. Eur J Cancer 2009; (45):228-47].

Acceptable imaging studies to evaluate disease at baseline include:

- Whole body PET-CT scan (except brain)
- Contrast-enhanced CT scan of neck, chest, abdomen and pelvis (and affected body part if needed).
- Brain imaging is to be done only at Screening and need not be repeated. For brain imaging an contrast enhanced MRI is ideal. If an MRI of the brain cannot be done (or is contraindicated) a contrast enhanced CT of the brain is acceptable.

A restaging PET-CT (preferred if possible, or CT) is required after completion of Prime Phase (+/- 2 weeks) and prior to definitive surgery (i.e. after the completion of induction doses of nivolumab and CMP-001). MRI brain is not required for follow up studies unless clinically indicated. Additional staging studies will be done as clinically indicated at the discretion of the treating physician. During the maintenance phase imaging studies will be done every 8 weeks (-/+ 2 weeks).

#### **7.1.4 Tumor Tissue Collection and Correlative Studies**

Planned correlative analyses will include flow cytometric analyses of tumor samples, TIL and peripheral blood mononuclear cells (PBMC), IHC analyses of pre-/post- treatment tumor samples, tumor whole exome/RNA sequencing. Single-cell RNA sequencing will be performed on a subset of treated patients. Studies will be performed under the direction of the Principle Investigator along with co-Investigator [name] in [name] lab.

##### Tumor tissue

Patients must undergo biopsy (e.g. punch or open biopsy) within 21 days (preferred; and up to 4 weeks) of entry to the study (baseline biopsy). Definitive surgery will be performed after 2 weeks of the third dose of nivolumab and any clinically indicated variation from this schedule should be discussed between the investigator, treating sub-investigator and surgical oncologist. Tumor tissue will be processed as described in the lab manual:

##### Primary melanoma (if available)

FFPE tissue block(s) or 10 unstained slides (air dried) from patients' originally resected primary melanoma will be requested as well.

##### Blood biospecimens

Blood biospecimens will be collected at baseline, and per the schedule outlined in Study Chart in **Section 6.1.**

At **EACH time point** please submit the following:

- One (1) 10mL RED top tube
- One (1) 8.5mL YELLOW top tube
- Eight (8) 10mL GREEN top tubes
- One (1) 2.5mL PAXgene DNA tube
- One (1) 2.5mL PAXgene RNA tube

At **Baseline and Week 12 ONLY** please submit the following:

- One (1) 2mL BD™ P100.

Each tube must be clearly labeled to include:

- Protocol number
- Patient sequence number

- Patient initials
- Originating institution/investigator name
- Date and time drawn
- Collection time point

### Stool specimens

Stool biospecimens will be collected at baseline, and per the schedule outlined in Study Chart in **Section 6.1**.

### Dietary questionnaire

DHQ-3 questionnaire may be administered electronically or on paper. Electronic administration is preferred. Data will be entered into DHQ-3 online per instructions as outlined in **Appendix 1**.

## 7.1.5 Laboratory Procedures/Assessments

Details regarding specific laboratory procedures/assessments to be performed in this trial are provided below. The total amount of blood/tissue to be drawn/collected over the course of the trial (from pre-trial to post-trial visits), including approximate blood/tissue volumes drawn/collected by visit and by sample type per subject can be found in the Procedures Manual.

### 7.1.5.1 Laboratory safety evaluations

Laboratory tests for hematology, chemistry, urinalysis, and others are specified in **Table 7.1.5.1-1**.

**Table 7.1.5.1-1: Laboratory Tests**

Hematology	Chemistry	Urinalysis	Other
Hematocrit Hemoglobin Platelet count WBC (total and differential including absolute neutrophil count)	Albumin Alkaline phosphatase Alanine aminotransferase (ALT) Aspartate aminotransferase (AST) Bilirubin (total; directly only if total is elevated above ULN) Total protein Blood urea nitrogen Bicarbonate Calcium Chloride Creatinine Glucose Phosphorus Potassium Magnesium Sodium Lactate dehydrogenase (LDH) Uric acid	pH Specific gravity Glucose Protein Blood Nitrites WBCs Microscopic battery (RBCs, WBCs, epithelial cells, casts) - only if significant positive findings on urinalysis	aPTT PT (INR) Serum or urine pregnancy test (β-human chorionic gonadotropin) + Thyroid function studies (thyroid stimulating hormone [TSH], Free T3, Free T4) # Autoimmune lab panel (anti-dsDNA, ANA, ANCA, RF, and anti-RNP) HIV \$ Hepatitis B surface antigen (HBsAg) and surface antibody (HBsAb) § Hepatitis C RNA (HCV RNA) §

+Perform on women of childbearing potential and at Screening only. If urine pregnancy results cannot be confirmed as negative, serum β-human chorionic gonadotropin will be required.

#Autoimmune lab panel will be performed at Screening and EOT only.

\$HIV, hepatitis B and C studies will be performed at Screening only in patients as clinically indicated.

Laboratory tests for screening should be performed within 28 days of registration. After W1D1, pre-dose laboratory procedures can be conducted up to 72 hours prior to dosing at the frequency

delineated in Section 6.1. Results must be reviewed by the investigator or qualified designee and found to be acceptable prior to each dose of trial treatment.

### **7.1.6 Other Procedures**

#### **7.1.6.1 Withdrawal and discontinuation**

When a subject discontinues/withdraws prior to trial completion, all applicable activities scheduled for the final trial visit should be performed at the time of discontinuation. Any adverse events which are present at the time of discontinuation/withdrawal should be followed in accordance with the safety requirements outlined in **Section 7.2 - Assessing and Recording Adverse Events**. The schedule for Post-Treatment Visits including Safety Follow-up Visits are delineated in **Section 7.1.7.2**. Following completion of treatment, patients will enter the Follow-Up Period of the study (described in **Section 7.1.7.2.2**).

#### **7.1.6.2 Blinding and unblinding**

Not applicable.

### **7.1.7 Visit Requirements**

Visit requirements are outlined in Section 6.0 - Trial Flow Chart. Specific procedure-related details are provided above in Section 7.1 - Trial Procedures.

#### **7.1.7.1 Screening**

##### Screening period

Screening starts with the subject's provision of a written informed consent and should be completed within 21 days (preferred; and up to 4 weeks) of initiation of study drug(s).

#### **7.1.7.2 Post-treatment surveillance**

Follow up period will start 12 weeks after the last on-treatment time point for patients have completed study treatments or discontinued study therapy for toxicity and have no disease progression. These patients are evaluated per the standard follow-up schedule including imaging (CT vs. CT/PET vs. PET at the discretion of the treating physician) at the intervals directed below. Every 3 months ( $\pm 2$  weeks) if patient is  $< 2$  years from start of follow up period, every 6 months ( $\pm 4$  weeks) if patient is 2-5 years from start of follow up period, and every 12 months ( $\pm 4$  weeks) if patient is  $> 5$  years from start of follow up period for up to 15 years. Patients who develop recurrent melanoma will be followed for information on survival and for information on salvage patterns. The schedule of clinical follow up for these patients will be at the discretion of the treating physicians and according to established Standard of Care. Adverse Events Assessment on the study will continue for all patients until 30 days after the last study drug administration.

#### **7.1.7.3 Safety follow up visit**

The mandatory Safety Follow-Up Visit should be conducted approximately 30 days after the last dose of trial treatment or before the initiation of a new anti-cancer treatment, whichever comes first. All AEs that occur prior to the Safety Follow-Up Visit should be recorded. Subjects with an AE of Grade  $> 1$  will be followed until the resolution of the AE to Grade 0-1 or until the beginning of a new anti-neoplastic therapy, whichever occurs first. SAEs that occur within 90 days of the end of

treatment or before initiation of a new anti-cancer treatment should also be followed and recorded.

#### **7.1.7.4 Follow up visit**

Subjects who discontinue trial treatment for a reason other than disease progression will move into the Follow-Up Phase and should be assessed by radiologic imaging to monitor disease status. Every effort should be made to collect information regarding disease status until the start of new anti-neoplastic therapy, disease progression, death, end of the study or if the subject begins retreatment with nivolumab as detailed in **Section 7.1.5.2.1**. Information regarding post-study anti-neoplastic treatment will be collected if new treatment is initiated.

#### **7.1.7.5 Survival follow up**

Once a subject experiences confirmed disease progression or starts a new anti-cancer therapy, the subject moves into the survival follow-up phase and should be contacted to assess for survival status until death, withdrawal of consent, or the end of the study, whichever occurs first. This will be done every 3 months.

### **7.2 Adverse and Serious Adverse Events**

#### **7.2.1 Definitions**

##### **7.2.1.1 Adverse events (AE)**

An AE is an untoward or medical occurrence associated with the use of study drug (active or placebo drug, biologic, or device) in clinical investigation subjects, which does not necessarily have a causal relationship with the study drug. An AE can therefore be any unfavorable and unintended symptom, sign, disease or condition, or test abnormality whether or not considered related to study drug. AEs that do not meet the definition for an SAE are considered non-serious AEs.

AEs include:

- Changes described by the subject or signs observed by the Investigator or medical staff.
- Test abnormalities (i.e., laboratory tests, ECGs) that result in an alteration in medical care (diagnostic or therapeutic).

Disease Progression is **not** considered an AE in this study.

Abnormalities present at baseline are considered AEs only if they reoccur after resolution or they worsen during the study.

##### **7.2.1.2 Serious adverse events (SAE) and serious unexpected adverse events (SUSAR)**

An SAE is any AE that fulfills one of the criteria outlined in **Table 7.2.1.2-1**.

**Table 7.2.1.2-1: Criteria for Determination of Serious Adverse Events**

Death	An AE that results in death. *In this study, deaths that are unequivocally due to Disease Progression are not to be reported as SAEs.
-------	---

Life-threatening AE	An AE that places the subject, in the view of the Investigator, at immediate risk of death from the AE as it occurred (i.e., does not include an AE that had it occurred in a more severe form, might have caused death).
Required or prolonged inpatient hospitalization	An AE that results in an initial inpatient hospitalization or prolongs an existing hospitalization of the subject. If a subject is hospitalized as part of the clinical use of the study drug, a period of normal hospitalization will be outlined in the protocol or by the judgment of the Investigator. Hospitalizations longer than this period will be prolonged hospitalizations.
Persistent or significant disability/incapacity	An AE that results in a substantial disruption of a subject's ability to conduct normal life functions.
Congenital anomaly/birth defect	A congenital anomaly/birth defect that occurs in the offspring of a subject exposed to the study drug.
Important medical event	An AE that may not result in death, be life-threatening, or require hospitalization may be considered an SAE when, based upon appropriate medical judgment, the event may jeopardize the subject and may require medical or surgical intervention to prevent 1 of the outcomes listed above.

Examples of such “important medical events” include allergic bronchospasm requiring intensive treatment in an emergency room or at home, blood dyscrasias or convulsions that do not result in inpatient hospitalization, or the development of drug dependency or drug abuse.

Medical and scientific judgment should be exercised in deciding whether expedited reporting is appropriate in other situations, such as with important medical events described above.

Events that meet SAE criteria must be recorded and reported regardless of expectedness or assessed association with study drug.

**Note:** Planned hospital admissions or surgical procedures for elective procedures or for an illness or disease that existed before the signing of the ICF or before the subject was enrolled in the study will not be captured as SAEs. If planned admissions or procedures occur at a time other than what was planned (i.e., due to an exacerbation in the preexisting illness or disease), they should be reported as SAEs.

### 7.2.1.3 Unexpected AE

An unexpected AE is any AE that is not consistent in specificity or severity with the current Investigator's Brochure (IB).

### 7.2.2 Evaluation of Adverse Events and Serious Adverse Events

The Investigator or designee is responsible for making an assessment as to the severity/grade (as defined in **Section 10.18.2.1**, below), causality/relationship (as defined in **Section 10.18.2.2**, below), and outcome of AEs and SAEs (as defined in **Section 10.18.2.3**, below). In addition, the Investigator or designee must report any actions taken as a result of an AE or SAE.

#### 7.2.2.1 AE severity/grade

For each recorded AE or SAE, the Investigator or designee must make an assessment of Grade using the Common Terminology Criteria for Adverse Events (CTCAE) version 4.03. Grade refers to the severity of the AE. Note that severity is not the same as “seriousness”. Seriousness (not severity) serves as a guide for defining regulatory reporting obligations.

### 7.2.2.2 Causality and relationship to study drug(s)

For each AE or SAE, the Investigator will determine whether there is a reasonable possibility demonstrated by evidence that suggests a causal relationship between the study drug regimen (CMP-001 plus nivolumab), and the AE according to the categories provided in **Table 7.2.2.2-1**. Attribution of adverse events specifically to either CMP-001 or nivolumab is challenging, therefore, the relationship to study drug should be based on attribution to the combination of the two drugs, not a single drug.

An AE with causal relationship not initially determined will require follow-up to assign causality which must be made by the Investigator prior to completion of the study. The Investigator may change his/her opinion of causality in light of follow-up information; if this occurs, the Investigator must amend the AE or SAE information accordingly.

**Table 7.2.2.2-1: Classifications for Adverse Event Causality/Relationship**

Classification	Definition
Unrelated	There is no suspicion of a causal relationship between exposure to the study drug regimen and the AE; another cause of the AE has been identified, no temporal association with study drug has been identified, or the study drug cannot be implicated.
Possibly related	There is some evidence supporting the possibility of a causal relationship between study drug regimen exposure and the AE; an alternative explanation (i.e., concomitant drug or concomitant disease) is inconclusive, the temporal association with study drug is reasonable, and the causal relationship cannot be excluded.
Probably related	An adverse event that has a timely relationship to the administration of the investigational drug regimen and follows a known pattern of response, but for which a potential alternative cause may be present.
Definitely related	There is strong evidence that there is a causal relationship between study drug regimen and the AE; the AE cannot be reasonably explained by an alternative explanation (i.e., concomitant drug or concomitant disease) and the temporal association with study drug is suggestive of a causal relationship.

An AE is considered related to treatment if the attribution is “possibly related”, “probably related”, or “definitely related.”

### 7.2.2.3 Classification of AE outcome

Adverse event outcome describes the status of the AE at the last observation. The Investigator will document the outcome of each AE or SAE using the categories provided in **Table 7.2.2.3-1**.

**Table 7.2.2.3-1: Classifications for Adverse Event Outcome**

Classification	Definition
Fatal	Termination of life as a result of an AE.
Not recovered/not resolved	Subject has not recuperated or the AE has not improved.
Recovering/resolving	Subject is recuperating or the AE is improving.
Recovered/resolved	Subject has recuperated, the AE resolved, or returned to baseline status / stabilized.
Recovered/resolved with sequelae	Adverse event has resolved, but the subject has been left with symptoms or pathology.
Unknown	Not known, not observed, not recorded, or refused.

#### 7.2.2.4 Action taken regarding AE

The Investigator will provide the action taken regarding study drug in response to the AE. Classifications for each of the potential actions taken are provided in **Table 7.2.2.4-1**. More than one option may apply to a single AE/SAE. For example, study drug may be delayed and the dose reduced in response to an AE. Action related to CMP-001 and nivolumab will be assessed and recorded separately in the EDC.

**Table 7.2.2.4-1: Classifications for Actions Taken Regarding an Adverse Event**

Classification	Definition
Dose not changed	No change in administration of study drug
Dose reduced 	Reduction in the amount of study drug administered
Study drug interrupted	Temporary interruption (termination) in administration of the study drug
Study drug withdrawn	Administration of the study drug terminated (no further dosing)
Not applicable	Determination of a value is not relevant in the current context
Unknown	Not known, not observed, not recorded, or refused

Refer to Section 5.2.1. and 5.2.3. regarding dose reductions of either Nivolumab or CMP-001 due to dose-limiting toxicities.

#### 7.2.3 Timeframe for Adverse Event/Serious Adverse Event Collection

The Investigator is required to record all AEs occurring during the clinical study (21 CFR 312.64[b] and ICH E6 [R1]) starting from the time the subject signs the ICF until 30 days after the last dose of CMP-001 on the AE page of the eCRF. SAEs that occur within 90 days of the end of treatment or before initiation of a new anti-cancer treatment should also be followed and recorded. SAEs as defined in Section 7.2.1.2. must also be reported to the Sponsor or its representative within 24 hours of knowledge of their occurrence, in accordance with Section 7.2.5.

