#### **5.2.2.4    CMP-001 Dose Modification**

CMP-001 will be dose-reduced in patients who develop CMP-001 related DLT and resume study therapy with Nivolumab/CMP-001 combination if Investigator determines that continued treatment with CMP-001 is in the subject's best interest. In this event, CMP-001 will be dose reduced as in **Table 5.2.2.3-1**.

[figure not shown]
CMP-001 will be withheld for CMP-001 related Grade 4 hematologic toxicities, non-hematological toxicity  $\geq$  Grade 3 including laboratory abnormalities, and severe or life-threatening AEs.

If CMP-001 is permanently discontinued for, subjects may continue to receive Nivolumab.

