## 5.7 Subject Withdrawal/Discontinuation Criteria

Subjects are free to withdraw from the study at any time and without penalty or loss of future medical care, or any other benefits to which they are otherwise entitled. Subjects may discontinue study medication for any of the following conditions:

- Dose-limiting or other unacceptable toxicity considered to be related to either study medication;
  - Patients who develop unacceptable toxicity deemed related to CMP-001 but not Nivolumab may continue Nivolumab after CMP-001 discontinuation for duration as defined in **Section 5.2.2.4**.
  - Patients who develop unacceptable toxicity deemed related to Nivolumab but not CMP-001 must discontinue **both CMP-001 and Nivolumab**.
- PD by RECIST (Version 1.1) if accompanied by medically significant clinical deterioration, in the judgment of the Investigator. (Continuation of treatment through suspected pseudo-progression is permitted.);
- If, in the opinion of the Investigator, it is medically necessary;
- Subject withdraws consent for the study (note that subjects who withdraw consent for additional study treatment and procedures will continue to be followed for long-term survival unless they explicitly withdraw consent for any follow-up);
- Subject develops an intercurrent illness or adverse event that precludes further participation, or requires a prohibited concomitant treatment;
- Subject becomes pregnant or begins breastfeeding;

- Subject is lost to follow-up.

Subjects discontinuing study medication earlier than planned or withdrawing from the study should undergo the subsequent End of Treatment (EOT) clinical and laboratory assessments as soon as possible after study medication is stopped and the requisite safety follow-up period of 30 days should also be followed. The reason for withdrawal will be recorded in the electronic case report form (eCRF) and the subject's source medical record. All subjects will continue to be followed every three months after the last CMP-001 treatment for long-term survival follow-up until death, loss to follow-up, or withdrawal of consent for follow-up.

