##### 7.2.3.1 Treatment-related AE

Treatment-related AE/SAE is defined as an AE that started or worsened in severity on or after the date the study drug was first administered. TEAE information will be collected from the time of the subject's first receipt of CMP-001 until 30 days after the last dose of CMP-001.

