##### 7.2.3.2 SAE

SAE information will be collected from the point the subject starts study treatment until 30 days after the last dose of CMP-001. If, at any time after the subject has completed participation in the study, the Investigator or study staff becomes aware of an SAE that they believe is possibly related or related to CMP-001 (see Section 7.2.1.2), then the event and any known details must be reported promptly to the Sponsor or its designee. The reporting instructions described in **Section 7.2.5** must be followed.

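### Section 7.2.3 ends adverse event collection 30 days after the last CMP-001 dose although nivolumab may continue alone, and its subsection 7.2.3.2 gives SAEs 30 days where 7.2.3 and 7.1.7.3 give 90.

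*Combined protocol and SAP*

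**What the plan says.** **Windows tied to CMP-001.** Section 7.2.3 records AEs from consent "until 30 days after the last dose of CMP-001 on the AE page of the eCRF". Section 7.2.3.1 collects treatment-emergent events from "first receipt of CMP-001 until 30 days after the last dose of CMP-001". Section 7.2.3.2 states: "SAE information will be collected from the point the subject starts study treatment until 30 days after the last dose of CMP-001". The flow chart in Section 6.1 monitors AEs to 30 days past end of treatment (EOT), and note B to the study calendar ties EOT to removal from CMP-001.

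**Nivolumab alone is allowed.** Section 5.2.2.4 says that after permanent discontinuation of CMP-001 "subjects may continue to receive Nivolumab". Section 5.7 says that patients with toxicity attributed to CMP-001 only "may continue Nivolumab after CMP-001 discontinuation", and note B repeats this.

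**Windows tied to study drug or trial treatment.** Section 7.1.7.2 continues AE assessment in all patients to 30 days after the last study drug. Section 7.1.7.3 requires a safety visit about 30 days after the last trial treatment, with all earlier AEs recorded. Section 7.1.3.1 also counts 30 days from the last study drug, but only for related and clinically significant AEs. Section 5.7 places the EOT "assessments as soon as possible after study medication is stopped", without singling out CMP-001.

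**SAE end.** Sections 7.2.3 and 7.1.7.3 also require follow-up and recording of "SAEs that occur within 90 days of the end of treatment" or before new anti-cancer treatment. Section 7.1.3.1 limits this to related SAEs. Section 7.2.3.2 stops at 30 days.

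**The concern.** Safety is a secondary objective (Section 3.2), and Section 8.5 tabulates each patient's maximum grade for every type of related toxicity. Those tables can hold only what the collection rule brings in. Section 7.2.3 is the section that staff would consult for that rule. Followed literally for a patient on nivolumab alone, it closes the AE page while the patient is still receiving a study drug. A related event that first appears after that date would be absent from the tables. Sites or data staff who work from Section 7.1.7.2 or 7.1.7.3 would record the same event, so ascertainment could differ between patients.

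The late-reporting clauses do not settle this. The one in Section 7.2.3.2 applies after the subject has completed participation, and only to "an SAE that they believe is possibly related or related to CMP-001". The one in Section 7.2.7 applies after discharge from the study.

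The SAE conflict does not depend on nivolumab continuing alone. It applies to every patient who reaches day 31 after the last dose.

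**Working it through.** **Planned schedule.** Sections 5.2.1.4 and 7.1.1 give a Boost Phase over weeks 12 to 56 with 12 CMP-001 doses and 23 (Q2W) or 12 (Q4W) nivolumab doses.

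- Every 4 weeks: (56 − 12)/4 + 1 = 12 doses, the last at week 56.
- Every 2 weeks: (56 − 12)/2 + 1 = 23 doses, the last at week 56.

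The stated counts are reproduced. Both drugs end together, so the planned AE-window difference is zero.

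**When CMP-001 stops early.** Assume nominal visit days and nivolumab on schedule to week 56. Day 1 of week w is study day 7(w − 1) + 1, so week 56 is day 386.

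- Section 7.2.3 closes at (last CMP-001 day) + 30.
- Section 7.1.7.2 closes at 386 + 30 = day 416.
- The difference is 416 minus the day on which 7.2.3 closes.

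| Last CMP-001 dose | Study day | 7.2.3 closes | Difference (days) | Nivolumab doses after closure, Q2W / Q4W |
|---|---|---|---|---|
| W3D1 | 15 | 45 | 371 | 23 / 12 |
| Week 12 | 78 | 108 | 308 | 20 / 10 |
| Week 32 | 218 | 248 | 168 | 10 / 5 |
| Week 48 | 330 | 360 | 56 | 2 / 1 |
| Week 52 | 358 | 388 | 28 | 0 / 0 |
| Week 56 | 386 | 416 | 0 | 0 / 0 |

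In the W3D1 row the three Prime Phase nivolumab doses (days 8, 22 and 36) fall inside the window and every Boost dose falls outside it. The difference includes the surgical interval, when no drug is given, and the 30 days after the last nivolumab dose.

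**SAE end when both drugs finish together.** 90 − 30 = 60 days between Section 7.2.3.2 and Sections 7.2.3 and 7.1.7.3, taking end of treatment as the last dose. Starting new therapy may shorten this. If its start is read as closing the 90-day period on day n, the difference is min(90, n) − 30: 30 days for n = 60 and 15 days for n = 45. The protocol does not state that reading for SAEs.

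**SAE end in the W3D1 case, with no new therapy.**

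- Section 7.2.3.2: 15 + 30 = day 45.
- Sections 7.2.3 and 7.1.7.3, if end of treatment means the end of CMP-001 as in note B: 15 + 90 = day 105.
- The same sections, if it means the last dose of either drug: 386 + 90 = day 476.

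**The case against.** The best defence is that a site complying with every section loses nothing. Section 7.1.7.2 covers all patients, the visit in Section 7.1.7.3 is mandatory and takes in all earlier AEs, Section 7.2.4 puts all AEs and SAEs on the eCRF, and Section 8.7 has weekly AE review. This makes a missed event less likely and points to the longer window as the intent. It does not remove the contradiction, because the section that sets the collection period says otherwise.

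The route to nivolumab alone may also be narrow. Section 7.2.2.2 asks for attribution to the combination, which sits awkwardly with a continuation rule that needs toxicity attributed to CMP-001 only. That stands as a reason to expect few such patients, but Sections 5.2.2.4 and 5.7 still provide for them.

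A reader might infer four stronger things that the documents do not support:

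- *That toxicity which worsens after the window closes is lost.* An event already recorded and unresolved is reviewed at later visits under Section 7.2.7, and Section 7.1.7.3 follows events above Grade 1. The exposure is mainly to new-onset events.
- *That all patients have an AE gap.* Under planned dosing there is none.
- *That the whole of Section 7.2.3 stops SAEs at 30 days.* Its opening paragraph gives them 90; only Section 7.2.3.2 stops at 30.
- *That the protocol already ends SAE collection at new therapy if that comes first.* Sections 7.1.3.1, 7.1.7.3 and 7.2.3 join the 90 days and the new treatment with a bare or. Where the protocol means the earlier of two dates, as for the safety visit or the ECI window in Section 7.2.5.2, it says so.

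**Conclusion.** The contradiction stands, in two parts. First, the AE and treatment-emergent AE windows in Sections 7.2.3 and 7.2.3.1 close before those in Sections 7.1.7.2 and 7.1.7.3 whenever nivolumab outlasts CMP-001. The difference runs from 28 days (last CMP-001 dose at week 52) to 371 days (W3D1), if nivolumab continues on schedule to week 56. The documents give no basis for estimating how many patients this concerns. Second, Section 7.2.3.2 conflicts with its own parent section on SAEs by up to 60 days, for every patient.

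The consequence is possible under-recording of new related events in a secondary safety analysis, at sites that follow Section 7.2.3 rather than Sections 7.1.7.2 and 7.1.7.3. The primary endpoint, major pathologic response, is not affected. The textual conflict is certain; its effect on the safety results is not known.

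A separate, minor point is that Section 5.8 requires a dose of both drugs for safety evaluability, Section 8.2 takes anyone who started treatment, and Section 8.5 names no population. The two definitions differ only for patients who never receive nivolumab.

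**What to change.** - In Sections 7.2.3, 7.2.3.1 and 7.2.3.2 and in note B, anchor data collection to the last dose of either study drug, whichever drug is given last.
- Collect all AEs, including SAEs, from consent to 30 days after that dose. This also settles the SAE start, which is consent in Section 7.2.3 and first treatment in Section 7.2.3.2, and the narrower AE scope in Section 7.1.3.1.
- Continue all SAEs to 90 days after that dose. State explicitly how the start of new anti-cancer treatment ends days 31 to 90, without shortening the first 30 days. A plain earlier-of rule would, for new therapy on day 10, stop SAE collection 20 days before the end now in Section 7.2.3.2.
- Align the flow chart, note B, note O (which starts the 30-day follow-up from completion of Boost cycle 12) and Sections 7.1.3.1, 7.1.7.2 and 7.1.7.3. Check consistency with the ECI window in Section 7.2.5.2.
- Separately, reconcile the safety-evaluable definitions in Sections 5.8 and 8.2 and name the population in Section 8.5.

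The 30-day and 90-day periods are already in the protocol, and no treatment rule changes. The cost is wording, a CRF completion note, modest extra AE entry for patients on nivolumab alone (who already attend for treatment), and a check of the records of patients already treated.
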